## LIST OF ABBREVIATIONS

AE	Adverse Event/Adverse Experience
CCH	Collagenase clostridium histolyticum
HIPAA	Health Insurance Portability and Accountability Act
IIEF	International Index of Erectile Function
PDE5s	Phosphodiesterase-5 inhibitors
PTT	Penile traction therapy
PD	Peyronie's Disease

**Study Summary**

Title	Efficacy of a Novel Collagenase Clostridium Histolyticum Protocol for Peyronie's Disease Among Prior Non-responders: A Randomized, Controlled, Single-blinded Study
IRB Protocol Number	20213914
Methodology	Prospective, randomized, controlled, single-blinded
Overall Study Duration	2 years
Subject Participation Duration	1 year
Objectives	Compare key clinical outcomes between controls and men treated with a novel CCH protocol among men previously unresponsive to CCH administration.
Number of Subjects	40
Diagnosis and Main Inclusion Criteria	Men >18 years of age with Peyronie's Disease, current curvature of 30 degrees or more, prior treatment with 6-8 injections of CCH, and prior minimal (<20% and/or <10 degrees) responsiveness to CCH administration.
Randomization	Patients will be randomized 1:3 to control (no treatment) or CCH (up to 8 injections). Patients in the control arm will subsequently be crossed over to CCH treatment after 6 months. Randomization tables will be created and pre-stratified based on baseline penile curvature.
Follow-up Period and Assessments	Men will have objective assessments of curvature and length and standardized and non-standardized questionnaires obtained at various time points (baseline, 6-weeks following completion of CCH, and at the end of the no treatment phase).
Statistical Methodology	Stratification of subjects prior to randomization to assure an equal representation based on baseline penile curvature (30-44, 45-59, 60-74, 75-89, 90 or above). Statistical comparisons between groups and to baseline will be made of responses to subjective questionnaires and objective measures.
Plan for Publication	It is anticipated that the primary study will be published following accumulation of data out to 1 year. Pending novelty of findings, additional studies may also be published if felt to be warranted (subset analyses).

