### 1.2 Investigational Treatments

The current study would randomize men 1:3 into one of two treatment cohorts: 1. Observation followed by CCH or 2. CCH followed by observation. This study design offers the benefits of a randomized,

controlled trial (highest level of evidence), while also providing data for a second set of publications evaluating the cross-over to treatment phase (for controls). RCTs are particularly important in PD, where the disease changes over time in a percentage of men as a function of its natural history. This would also allow blinding of measurements using photographs (single-blinded assessments), which provides further study rigor. See Figure 1 for overall study schema.

1. No treatment (control) followed by CCH. Men in this cohort would undergo baseline assessments followed by no treatment for 6 months and then repeat assessments. Men would then cross-over to CCH treatment and undergo up to 8 injections (or until curvature is <15 degrees). Interval assessments would be performed with the 1st injection of each series, and final assessments would then be performed 6 weeks following the final injection.
2. CCH followed by no treatment. Men in this cohort would undergo baseline assessments followed by up to 8 injections of CCH (or until curvature is <15 degrees). Interval assessments would be performed with the 1st injection of each series and 6 weeks following completion of treatment. Men then would not undergo any additional treatments for 6 months, after which final assessments would then be performed.

During CCH administration, several key differences from the IMPRESS protocols would be performed. Please note that each of these changes have been slowly implemented in the investigators' practice over time to improve overall efficacy of therapy:

	IMPRESS Protocol	Current Study Protocol
Amount administered	0.58 mg	0.9 mg
Suspension volume	0.37 ml	0.7 ml
Method of injection	Into plaque	To point of maximal curvature in the tunica, as determined with an erection at the first injection of each series
Administration schedule	1-3 days apart	1 day apart
Mechanical device traction	None	RestoreX 30-60 min daily until 6 weeks after final injection
Office modeling	Performed 1-3 days after initial injections (defined as "firm")	10-15 lbs of force performed at the time of 2 nd injection

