### 3.6 Randomization Protocol

Following enrollment and completion of the consent, a length and curvature assessment will be performed as well as baseline questionnaires. Men will then be randomized based on a previously created randomization table that takes into account baseline curvatures (see attached Randomization Table). Groupings are divided based on initial curvature of 30-44, 45-59, 60-74, 75-89, 90 or above to assure equal representation in each study arm. Men will then undergo treatment as noted above.

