### **5.2 Statistical Analysis**

The current study is considered exploratory in nature. Analyses will be performed using comparisons within and between patient cohorts. All captured data will be utilized as a point of comparison based on accepted standards (e.g. IIEF subdomains, PDQ subdomains, etc.). All data will be analyzed to determine if it is normative / non-normative and will be described and compared appropriately (mean, SD versus median, IQR).

Patients with partial missing data will have all available data included for analysis, with no attempts made to statistically replace missing variables. All data will be analyzed using an intent-to-treat analysis.

Adverse events will be reported as a total as well as compared between cohorts.

A power analysis was performed using historical data from another one of the investigators' RCTs to determine the standard deviation for control men between two sequential assessments. Results of absolute curvature improvements demonstrated a standard deviation of 16 degrees or 27% relative improvement. Using a 0.05 alpha threshold, power of 80%, and expected cohort size of 30 (assuming 30 with 6-month data) this would allow us to distinguish differences over 17 degrees or 29%. Given the investigators' current improvements of 60% with the investigators' preliminary data, we would expect this study to have sufficient power to demonstrate a clinically and statistically significant finding.

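### Subset analyses may be published depending on the novelty of what they show, with no commitment to report every subset examined

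*Combined protocol and SAP*

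**What the plan says.** The Plan for Publication row of the Study Summary treats two kinds of paper differently. For the main paper it says "It is anticipated that the primary study will be published following accumulation of data out to 1 year", with no reference to what the data show. For further papers it says "Pending novelty of findings, additional studies may also be published if felt to be warranted (subset analyses".

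Section 5.2 opens with "The current study is considered exploratory in nature" and continues "Analyses will be performed using comparisons within and between patient cohorts". It names no patient subset, interaction test or multiplicity rule, and does not undertake to report every subset examined. The endpoint lists in 2.1 and 2.2 contain no subgroup comparison.

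Two baseline groupings exist but have no analysis rule. Section 3.6 defines curvature bands for randomization: "Groupings are divided based on initial curvature of 30-44, 45-59, 60-74, 75-89, 90 or above". Section 4.2 grades plaque calcification as none, mild, moderate or severe, and 3.1.2 excludes severe calcification, which leaves three eligible grades.

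One further line of publication is foreseen without a novelty condition. Section 1.2 describes the design as "while also providing data for a second set of publications evaluating the cross-over to treatment phase (for controls", and secondary outcomes 2 to 5 in 2.2 list those comparisons.

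**The concern.** Novelty is a property of the result. If a subset paper goes forward because its finding is novel, the published estimates are a selected sample of those computed. That raises the chance that a published subset finding is false, and it biases the published effect upwards.

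Both problems grow as subsets shrink, and this trial is small, with allocation stated as "Patients will be randomized 1:3 to control (no treatment) or CCH (up to 8 injections". Forty men give 40/4 = 10 controls, and 30 men with outcomes give 7 or 8. If the number of subsets examined is not disclosed, a reader cannot correct for the selection. The plan does not require that disclosure.

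**Working it through.** **Inputs from the documents.** Up to 40 enrolled and at least 30 with outcomes (3.4); 1:3 allocation (Study Summary); SD of curvature change 16 degrees, alpha 0.05, 80% power and a detectable difference of 17 degrees (5.2); five curvature bands (3.6); three eligible calcification grades (3.1.2 and 4.2).

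**Assumptions, because the documents give no figure.** The number of subsets examined; independence between looks; five equally filled curvature bands; two-sided tests.

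**The plan's own figure.** A two-sample t-test with SD 16 and 80% power gives a detectable difference of 16.96 degrees for 15 v 15 men and 16.8 degrees for 10 v 30, so 17 degrees reproduces under either split. (For 30 men split 1:3 the two-sided figure is 19.6 degrees. That is a separate matter.) The publication sentence itself carries no figure to reproduce.

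**Step 1: false positives over k looks.** With no true effect, P(at least one p < 0.05) = 1 − 0.95^k.
- k = 5 (for example, the curvature bands): 1 − 0.95^5 = 0.226.
- k = 8 (five bands plus three grades): 1 − 0.95^8 = 0.337.

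The eight looks are not truly independent, since each man has both a band and a grade. A simulation of 40 men cross-classified in this way gave about 32%, so the assumption matters little.

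**Step 2: precision within one stratum.** One of five equal bands among 40 men holds 8 men, 2 controls and 6 treated.
- SE = 16 × √(1/2 + 1/6) = 13.06 degrees.
- Critical value t(6 df, 0.975) = 2.447.
- With the observed SD at 16, the difference needed for significance is 2.447 × 13.06 = 32.0 degrees.

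**Step 3: exaggeration among significant results in that stratum** (noncentral t for power, simulation for the mean significant estimate).

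| True difference (degrees) | Power | Mean significant estimate (degrees) | Ratio to truth |
|---|---|---|---|
| 17 | 0.20 | about 32 | 1.9 |
| 30 | 0.49 | about 39 | 1.3 |
| 33.8 | 0.58 | about 41 | 1.2 |

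The 17 is the detectable difference in 5.2. The 33.8 is the mean improvement with combined therapy cited in 1.1, used only to mark the upper part of a range. It is a within-group change, not a difference from control.

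**Step 4: selecting the largest of five strata.** With SE 13.06 in each, the largest of five estimates averages about 32 degrees when every true difference is 17, and about 15 degrees when every true difference is zero.

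**Sensitivity.** Larger subsets do better. A half-sample of 5 v 15 men has power of about 0.50 at 17 degrees. With 30 men, a one-fifth stratum averages 1.5 v 4.5 men and power falls to about 0.14.

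**The case against.** The strongest reply is that this is one permissive line in a summary table. It says subset papers may appear, not that they will, and it does not say that unremarkable subsets will be withheld. That stands as far as it goes: a reader might infer a commitment to publish subsets, or to drop the dull ones, and the text supports neither. The condition attached to the permission still depends on the result.

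A reader might also take the sentence in 5.2, "All captured data will be utilized as a point of comparison based on accepted standards", as licence to compare any patient subgroup. It does not support that. Its examples are IIEF and PDQ subdomains, so it concerns outcome scales, and the units of comparison in that section are cohorts. The point rests on the Study Summary sentence and on the absence of any offsetting rule.

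The term for subset analyses is undefined, and the additional papers might partly mean the cross-over publication. That reading is possible but does not remove the point, because 1.2 foresees the cross-over papers without a novelty condition.

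The study is declared exploratory. That lowers the weight of any subset result but does not show how many subsets were examined or set aside.

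Finally, the illustrations use an assumed number of looks and assumed equal strata, and the exaggeration is much smaller if the true effect is large. This is correct, and is why a range is shown. Section 5.2 expects a large effect, citing about 60% improvement in preliminary data.

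**Conclusion.** The concern holds in a limited form. The plan makes publication of subset analyses depend on what they show, and nothing elsewhere requires every subset examined to be reported. The primary and secondary endpoints, the sample size and the main paper are untouched.

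The size is illustrative: a 23% to 34% chance of at least one false positive over 5 to 8 independent looks with no true effect, and exaggeration of about 1.9-fold at a true 17 degrees, falling to about 1.2-fold at 34 degrees, in an assumed 2 v 6 stratum with SD 16. These figures rest on the assumed number of looks and on equal strata; the documents give neither a list of subsets nor a curvature distribution.

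A reader might infer that any published subset finding will be unreliable. The documents do not support that. It depends on how many subsets are examined, how large they are, how large the true effect is, and what a future paper discloses.

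**What to change.** In the Plan for Publication, delete the novelty condition and state:

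> Any subset analysis will be labelled exploratory, and every subset examined will be reported with its estimate and 95% CI whatever the result, stating the number examined and which were chosen after seeing the data.

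Repeat or cross-refer to this in 5.2 so that it sits with the analysis rules.

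The cost is wording only: no added visits, data or patients. The downside is less freedom to publish selected subset papers.

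Naming baseline curvature and calcification grade as the only subsets, each with an interaction test, is optional. Such tests would be weak here: by the normal approximation, a two-subset interaction with equal halves and SD 16 needs a difference between subset effects of about 33 degrees (40 men) to 38 degrees (30 men) for 80% power. Full disclosure addresses the selection without them.

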## 1 Introduction

This document is a protocol for a randomized, controlled, single-blinded clinical trial. This study will be carried out in accordance with the procedures described in this protocol, applicable United States government regulations and Western International Review Board policies and procedures.

### 1.1 Background and Clinical Need for the Current Study

Collagenase Clostridium histolyticum (CCH) is the first FDA approved medication for the treatment of Peyronie's Disease and demonstrated significant improvements in penile curvature and both in two phase III trials. Results specifically demonstrated a mean 34%, or 17-degree improvement in curvature. Post-FDA release, multiple series, including the investigators' own data have confirmed similar findings, including among men with ventral curvatures and calcification.

Beginning approximately 3 years ago, the investigators' team sought to achieve further improvements with CCH through the addition of more aggressive modeling therapies. Results from a comparison of CCH alone vs CCH and traction with RestoreX demonstrated a mean 33.8 degree (49%) curvature improvement with combined therapy compared to 19-20 degrees (30-31%) with CCH alone or CCH and other traction devices. These results currently represent the greatest improvements with CCH in published literature and further build upon phase IIb results which demonstrated that mechanical traction (via manual modeling in the phase IIb trial) represents a critical factor in achieving improvements with CCH.

The investigators' team additionally published a survey of men who had experienced suspected penile fractures with CCH and demonstrated greater curvature improvements without any loss / worsening of erectile function. This critical study highlighted that conservative management of suspected fractures should not only be considered a standard of care in managing suspected fractures, but also that these men achieved better final outcomes (again highlighting the importance of the combination of mechanical curvature correction in addition to CCH management).

Based on the above findings, the investigators' team began performing a more aggressive manual modeling protocol. This novel protocol included several notable innovations: dilution of the 0.9 mg of CCH in 0.7 ml of diluent, injection to the erect penis to assure accurate injection, repeat curvature assessments with each series (due to changing of the point of maximal curvature), incorporation of RestoreX traction therapy post injection, and 'aggressive' manual modeling (equivalent of 10-15 lbs of force) to achieve curvature correction. Preliminary (unpublished – abstract submitted to SMSNA 2021) results from these men demonstrated a median ~60% curvature improvement. Importantly, several of the patients had previously undergone 8 CCH injections with outside providers and were able to similarly achieve a median 60% improvement with the investigators' injection / modeling protocol.

### 1.2 Investigational Treatments

The current study would randomize men 1:3 into one of two treatment cohorts: 1. Observation followed by CCH or 2. CCH followed by observation. This study design offers the benefits of a randomized,

controlled trial (highest level of evidence), while also providing data for a second set of publications evaluating the cross-over to treatment phase (for controls). RCTs are particularly important in PD, where the disease changes over time in a percentage of men as a function of its natural history. This would also allow blinding of measurements using photographs (single-blinded assessments), which provides further study rigor. See Figure 1 for overall study schema.

1. No treatment (control) followed by CCH. Men in this cohort would undergo baseline assessments followed by no treatment for 6 months and then repeat assessments. Men would then cross-over to CCH treatment and undergo up to 8 injections (or until curvature is <15 degrees). Interval assessments would be performed with the 1st injection of each series, and final assessments would then be performed 6 weeks following the final injection.
2. CCH followed by no treatment. Men in this cohort would undergo baseline assessments followed by up to 8 injections of CCH (or until curvature is <15 degrees). Interval assessments would be performed with the 1st injection of each series and 6 weeks following completion of treatment. Men then would not undergo any additional treatments for 6 months, after which final assessments would then be performed.

During CCH administration, several key differences from the IMPRESS protocols would be performed. Please note that each of these changes have been slowly implemented in the investigators' practice over time to improve overall efficacy of therapy:

	IMPRESS Protocol	Current Study Protocol
Amount administered	0.58 mg	0.9 mg
Suspension volume	0.37 ml	0.7 ml
Method of injection	Into plaque	To point of maximal curvature in the tunica, as determined with an erection at the first injection of each series
Administration schedule	1-3 days apart	1 day apart
Mechanical device traction	None	RestoreX 30-60 min daily until 6 weeks after final injection
Office modeling	Performed 1-3 days after initial injections (defined as "firm")	10-15 lbs of force performed at the time of 2 nd injection
Home modeling	3x daily modeling performed, gentle attempts at straightening erection	10-15 lbs of force performed at least one daily; straightening during erection
Penile wrapping	No comments	Mandatory x 5 days after 2 nd injection of each series

### 1.3 Preliminary Data

Please refer to the introductory section for a more complete description of preliminary data. The investigators' team has been implementing the above, novel techniques in a step-wise fashion over time. Data from men who have been treated since Jan 2020 demonstrates a median improvement of ~60% (compared to 30% with prior series). Importantly, this series included several patients who had

previously undergone prior CCH injections with other providers. These findings suggest a proof of concept for the novel approach and would represent the largest improvement in curvature ever achieved with CCH. Findings would also benefit Endo Pharmaceutical, as it would provide proof of concept data that additional series of CCH may be merited in many cases of men with PD.

## **1.4 Study Rationale and Risk Analysis (Risks to Benefits Ratio)**

### **1.4.1 Study Rationale**

As noted previously, the investigators' team had previously performed a survey of men who experience suspected fractures with CCH and showed greater curvature correction without worsening of erectile function. More recent preliminary data from the investigators' prospective cohort also demonstrated significantly improved outcomes with the protocol described above without any worsening of complications compared to historical series (SMSNA abstract 2021). These findings suggest data sufficient to perform a more rigorous study evaluating the use of CCH with this modified protocol.

### **1.5 Anticipated Duration of the Clinical Investigation**

The overall study will be scheduled for approximately 1 year. Depending on the duration of CCH administration, this time period may fluctuate by several months.

## **2 Study Endpoints**

### **2.1 Primary Endpoints**

1. Compare penile curvature between control and treatment groups at 6 months
2. Compare PDQ outcomes between control and treatment groups at 6 months

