### **2.2 Secondary Outcomes**

1. Compare IIEF outcomes between control and treatment groups at 6 months
2. Compare penile curvature changes in control men at baseline and 12 months (i.e. prior to and following cross-over to CCH)
3. Compare penile length changes in control men at baseline and 12 months (i.e. prior to and following cross-over to CCH)
4. Compare PDQ changes in control men at baseline and 12 months (i.e. prior to and following cross-over to CCH)
5. Compare IIEF changes in control men at baseline and 12 months (i.e. prior to and following cross-over to CCH)
6. Compare penile length changes between control and treatment groups at 6 months
7. Report adverse events at 6 and 12-month time points

8. Report changes in penile curvature between 6 and 12-month assessments for CCH men

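### The plan does not say how baseline scores enter the between-group 6-month PDQ (primary) and IIEF comparisons, and names no baseline adjustment although both scores are collected before randomisation

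*Combined protocol and SAP*

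**What the plan says.** Section 2.1, item 2, makes PDQ a primary endpoint: "Compare PDQ outcomes between control and treatment groups at 6 months". Section 2.2, item 1, reads "Compare IIEF outcomes between control and treatment groups at 6 months". Neither mentions change or baseline. Other items in the same list do: item 6 is "Compare penile length changes between control and treatment groups at 6 months", and item 4 is "Compare PDQ changes in control men at baseline and 12 months".

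The baseline scores will exist. The assessment table in section 3.5 marks PDQ and IIEF at baseline, and section 3.6 says that, before randomisation, "a length and curvature assessment will be performed as well as baseline questionnaires". The strata in section 3.6 are bands of baseline curvature only.

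On analysis, the Study Summary says "Statistical comparisons between groups and to baseline will be made of responses to subjective questionnaires and objective measures". Section 5.2 says "Analyses will be performed using comparisons within and between patient cohorts" and "All data will be analyzed to determine if it is normative / non-normative and will be described and compared appropriately". It names no test, change score or covariate for PDQ or IIEF.

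**The concern.** Three analyses fit this wording: the 6-month score, the change from baseline, and the 6-month score adjusted for baseline. They have different precision and, in a given sample, different estimates. On a primary endpoint the choice should not be open once data are in hand.

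The choice matters more here because the control arm is small. Thirty evaluable men at 1:3 give about 7 or 8 controls against 22 or 23 CCH men. Curvature stratification balances PDQ and IIEF only as far as they track curvature. If the arms differ by chance in how bothered the men were at entry, an unadjusted 6-month comparison reports part of that difference as treatment effect. Section 5.2 gives no power for PDQ or IIEF, so there is no demonstrated margin to absorb avoidable variance.

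**Working it through.** **Inputs from the documents.** Allocation 1:3 (Study Summary); up to 40 men enrolled to obtain at least 30 with outcomes (3.4); alpha 0.05, power 80%, 30 men with 6-month data, SD of curvature improvement 16 degrees or 27% (5.2).

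**Assumptions.** The documents give neither an SD for PDQ or IIEF nor a within-arm baseline-to-6-month correlation, rho. Results are therefore in SD units, with equal SDs at both times and in both arms, and rho from 0.3 to 0.8. Tests are two-sided; section 5.2 does not state sidedness. Arm sizes are 30/4 = 7.5 and 22.5.

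**1. The plan's own figure.** Section 5.2 states a detectable curvature difference of 17 degrees or 29%. A two-sided t-test with 15 versus 15 men gives 16.96 degrees and 28.6%, which matches. At the planned 1:3 split the two-sided result is 19.6 degrees and 33.0%; a one-sided test at 1:3 gives 17.2 degrees and 29.0%. That mismatch is a separate matter. The figure covers curvature only, so there is nothing to reproduce for PDQ or IIEF.

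**2. Chance baseline difference.** Its standard error is sqrt(1/7.5 + 1/22.5) = 0.422 SD. The probability of a difference above 0.5 SD in either direction is 2 × P(Z > 0.5/0.422) = 2 × P(Z > 1.186) = 0.236. With all 40 men (10 versus 30) the standard error is 0.365 SD and the probability is 0.171.

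**3. What an unadjusted comparison carries.** Given a baseline difference d, the expected shift in the 6-month difference is rho × d. For d = 0.5 SD this is 0.15 SD at rho 0.3, 0.30 SD at 0.6 and 0.40 SD at 0.8.

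**4. Precision of the three analyses.** Residual variance relative to the 6-month score is 1 for the score itself, 2(1 − rho) for the change, and 1 − rho² with adjustment for own baseline. The detectable difference at 80% power (noncentral t; 28 df for the first two analyses, 27 df for the adjusted one) is:

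| rho (assumed) | 6-month score | Change score | Adjusted for baseline |
|---|---|---|---|
| 0.3 | 1.22 SD | 1.45 SD | 1.17 SD |
| 0.4 | 1.22 SD | 1.34 SD | 1.12 SD |
| 0.5 | 1.22 SD | 1.22 SD | 1.06 SD |
| 0.6 | 1.22 SD | 1.09 SD | 0.98 SD |
| 0.7 | 1.22 SD | 0.95 SD | 0.88 SD |
| 0.8 | 1.22 SD | 0.77 SD | 0.74 SD |

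The change score loses to the 6-month score below rho 0.5, because 2(1 − rho) then exceeds 1. The adjusted analysis is best in every row.

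**5. Cost of estimating the slope.** On average this multiplies the adjusted variance by 1 + 1/(30 − 4) = 1.038, so the last column rises by about 2% (sqrt(1.038) = 1.019): 1.19 SD at rho 0.3 and 0.75 SD at rho 0.8. The adjusted analysis still wins throughout the range.

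**The case against.** The strongest objection is that the documents never say 6-month scores are compared without reference to baseline. The Study Summary names questionnaires and baseline in one sentence, and section 5.2 foresees within-cohort as well as between-cohort comparisons. The contrast between outcomes and changes is also weak evidence of intent: primary endpoint 1 likewise names curvature at 6 months without mentioning change, yet section 5.2 powers it on an SD of improvement. Loose drafting is a plausible explanation. This stands. A reader might infer that the plan commits to raw scores; that is the most natural reading of two items, but it is not stated. What remains is that the measure is undefined.

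Second, randomisation makes a baseline difference a matter of chance, and an unadjusted test is valid on average. This also stands. A reader might infer systematic bias, and nothing in the documents supports that. Nor are the shift in step 3 and the precision loss in step 4 two separate harms: they are the same rho² share of variance, seen conditionally on one sample and averaged over samples.

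Third, the size of the gain rests on an assumed rho, and at 0.3 it is small. True, which is why the range is shown.

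Fourth, section 5.2 calls the study exploratory. It also designates primary endpoints, sets alpha and power, and expects a statistically significant result, so defining the primary measure is still worthwhile.

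Finally, a reader might count between-group length as another instance. It is not: item 6 is already worded as a change.

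**Conclusion.** The point holds as a gap in specification with a better analysis available from data already collected. The plan does not define the between-group PDQ or IIEF measure and names no baseline adjustment. The chance figures of 24% with 30 men and 17% with 40 rest only on the arm sizes and a normal approximation. The gain in detectable difference, from 1.22 SD to between 1.17 and 0.74 SD, rests also on rho between 0.3 and 0.8 and equal SDs, neither of which the documents supply. The recommendation does not depend on which analysis the sponsor had in mind: over that range, own-baseline adjustment is more precise than either the 6-month score or the change. Confidence is high that no adjustment is named, and lower on how much precision is at stake.

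**What to change.** In section 2.1 item 2, section 2.2 item 1 and section 5.2, state that the 6-month PDQ and IIEF comparisons are regressions of the 6-month score on randomised arm plus the same score's own baseline value, reported as the adjusted mean difference with its 95% confidence interval. Name which PDQ score is primary, since section 5.2 refers to subdomains. Because section 5.2 foresees non-normal data, specify a rank-based version of the same model for clearly non-normal scores, and write down beforehand the rule for switching to it.

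Using the same model for between-group length (section 2.2 item 6) is an optional gain in efficiency.

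The cost is wording and one degree of freedom per model. Section 5.2 rules out replacing missing values, so a man without a baseline score drops out of that model; this should be rare, since baseline questionnaires precede randomisation. No new visits, data or patients are needed.

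### Two unranked primary endpoints, no named PDQ score and no rule linking the tests: if either endpoint may carry a claim at 0.05, the family-wise error is about 8-10%, not 5%.

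*Combined protocol and SAP*

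**What the plan says.** Section 2.1 gives two primary endpoints: "Compare penile curvature between control and treatment groups at 6 months" and "Compare PDQ outcomes between control and treatment groups at 6 months". They are numbered, but nothing says the numbers are a ranking. The section names no PDQ score or summary and does not say whether a positive trial needs one endpoint or both.

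Section 5.2 says: "All captured data will be utilized as a point of comparison based on accepted standards (e.g. IIEF subdomains, PDQ subdomains, etc". The only significance level in the document is in the power statement of the same section: "Using a 0.05 alpha threshold, power of 80%, and expected cohort size of 30 (assuming 30 with 6-month data". Its inputs and result are for curvature alone: "Results of absolute curvature improvements demonstrated a standard deviation of 16 degrees or 27% relative improvement", and "this would allow us to distinguish differences over 17 degrees or 29" percent. Section 5.2 contains no multiplicity adjustment, alpha split or testing order.

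The section opens by describing the study as exploratory. It closes by expecting enough power for a result that is both statistically significant and clinically meaningful.

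Section 1.2 describes blinding only for measurements taken from photographs, and the control arm receives no treatment. Section 4.2 lists PDQ among the questionnaires. Only the adverse-event form there is reserved for study personnel, so PDQ is presumably completed by the men themselves.

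**The concern.** With two primary endpoints and no success rule, the plan leaves open what counts as a positive trial. An author following it could report success on curvature, on PDQ, or on whichever PDQ subdomain gave the smallest p-value, and each choice would be compatible with the text. If any one of these suffices at 0.05, the error rate for the primary claim as a whole exceeds 5%.

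A separate weakness affects which endpoint should lead. PDQ has no stated SD, target difference or power. It is a questionnaire answered by men who know whether they were treated, so blinded reading of photographs does not protect it. Without a ranking, it has the same standing as the endpoint that was powered and can be read blind.

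**Working it through.** **The plan's own figure.** Inputs from Section 5.2: SD 16 degrees or 27%, alpha 0.05, power 80%, 30 men with 6-month data. Sidedness is not stated. The detectable difference D solves 1 - F(t_crit; 28 df, noncentrality D/SE) = 0.80, where F is the noncentral t distribution and SE = SD x sqrt(1/n1 + 1/n2).

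- Two-sided, 15 per arm: SE = 16 x sqrt(2/15) = 5.84, giving D = 16.96 degrees. With SD 27%, D = 28.6%. This matches the plan's 17 degrees and 29%.
- One-sided, 7.5 and 22.5 (the planned 1:3 allocation): D = 17.2 degrees and 29.0%, which also matches.
- Two-sided, 7.5 and 22.5: SE = 16 x sqrt(1/7.5 + 1/22.5) = 6.75, giving D = 19.6 degrees and 33.0%.

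The figure is therefore reproducible and uses curvature inputs only. Whether it fits the 1:3 allocation is a separate question.

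**Error rate for two endpoints.** Assumptions: each is tested at two-sided 0.05, either one suffices for a claim, and treatment has no effect on either.

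- Independent tests: 1 - 0.95^2 = 9.75%.
- Upper limit under any correlation: 0.05 + 0.05 = 10%.
- Simulated correlated z-tests (500,000 replicates): 9.1% at correlation 0.5 and 8.3% at 0.7.
- If both endpoints must be significant: at most 5%, because the chance that both are falsely significant cannot exceed the chance for one.

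**If PDQ subdomains may also count.** The documents do not give the number of subdomains, so the number of qualifying tests k is an assumption. The independent column is 1 - 0.95^k. The others are simulated with all pairwise correlations equal.

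| k | Independent | Correlation 0.5 | Correlation 0.7 |
|---|---|---|---|
| 2 | 9.75% | 9.1% | 8.3% |
| 3 | 14.3% | 12.6% | 10.9% |
| 4 | 18.5% | 15.6% | 13.1% |
| 5 | 22.6% | 18.3% | 14.9% |

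Only the k = 2 row rests on a count found in the plan.

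**Error rate under a fixed sequence, curvature first.** If curvature has no true effect, any false claim requires a false rejection on curvature or a PDQ test reached through one, so the error is at most 5%. If curvature has a true effect and PDQ does not, the only possible false claim is the single PDQ test at 0.05, again at most 5%.

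**The case against.** The strongest reply is that the study is declared exploratory, expects about 30 evaluable men, and so does not need strict family-wise control. That reduces the stakes. It does not settle the matter, because the plan names primary endpoints, powers one of them and expects statistical significance. The closing expectation follows the curvature figures, however. It is a statement about power, not a promise of success on PDQ.

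Second, the plan never says that either endpoint alone suffices. If both were required there would be no inflation. This is correct, and the 8-10% is conditional for that reason. But the plan does not state the both-required rule, and that rule would need a power basis for PDQ, which is absent.

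Third, 0.05 is never given as the decision threshold for PDQ. That too is correct. Applying it to PDQ is an inference from the only level the document contains.

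A reader might go further and infer a false-positive rate of 10-23%. The documents do not support the upper end. It needs five qualifying tests, and the number of PDQ subdomains appears nowhere. It needs each subdomain to count as a primary test, whereas the sentence in Section 5.2 covers all captured data, including IIEF, which is secondary. It also needs independence, which is unlikely among parts of one questionnaire.

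A reader might also treat PDQ's lack of power and blinding as causes of the inflated rate. Low power does not raise the false-positive rate, and reporting bias is not part of the calculation above.

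**Conclusion.** The concern holds in a limited form. The plan has two unranked primary endpoints, an undefined PDQ outcome and no rule linking the tests. If either endpoint may support a claim at two-sided 0.05, the family-wise error is about 8-10%, for correlations from 0.7 down to zero. It rises by an amount the documents do not fix if any PDQ subdomain qualifies, and it is at most 5% if both endpoints are required. The result rests on the either-suffices reading and on applying 0.05 to PDQ, neither of which the plan states or excludes. The exploratory label makes this a worthwhile clarification rather than a fatal defect. The absence of a power basis and of blinding for PDQ supports placing it second.

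**What to change.** Add one paragraph to Section 5.2 and align Section 2.1 with it:

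- Test one named curvature measure first at two-sided 0.05. The measure must be chosen, because Section 4.2 assesses two planes and Section 5.2 uses both degrees and percent.
- Test one named PDQ score at two-sided 0.05 only if curvature is significant.
- Report the remaining PDQ and IIEF subdomains descriptively with confidence intervals.
- State that the power figure applies to curvature only.
- State as a limitation that PDQ is reported by men who know their arm. The sequence does not remove that bias.

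The cost is wording only: no added patients or visits, and no curvature power lost to the ordering. The downside is that no formal PDQ claim is possible if curvature is not significant. The preliminary 60% improvement should not be used to dismiss that risk: Section 1.1 calls the results unpublished, says only that several of the men had received 8 earlier injections, and does not say those men were non-responders.

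Other rules would also control the error, and the choice depends on what the sponsor intends. Requiring both endpoints would need a power calculation for PDQ. Splitting alpha at 0.025 each gives 1 - 0.975^2 = 4.9% for independent tests, but costs curvature power. With 15 per arm, the detectable difference rises from 17.0 to 18.9 degrees, and power for 17 degrees falls from 80% to 70%. With a two-sided test at 1:3 it rises from 19.6 to 21.8 degrees, and power for 17 degrees falls from 68% to 57%. The 19.6 is this review's calculation for that allocation, not the plan's figure.
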